3.5.2 Medical History

Medical history data will be coded by using the Medical Dictionary for Regulatory Activities (MedDRA) Version 20.0. The codings will be reviewed by qualified medical personnel, and then summarized by system organ class (SOC) and preferred term (PT) and by the medical history status “Ongoing”, or “Resolved” by treatment group and for all subjects. If a subject reports more than one SOC/PT, that subject will be counted only once toward the status “Ongoing” for the summary of that SOC/PT.

3.5.3 Gynecological History

Gynecological history data will be summarized for key parameters collected in the CRF, with categorical (qualitative) parameters as:

- Is there a history of Bacterial Vaginosis?
- Is there a history of Sexually Transmitted Infections?

and continuous (quantitative) parameters as:

- Approximate number of times (per month) you have vaginal intercourse
- Current total number of sexual partners

The number and percentage of ITT subjects will be provided by treatment group and for all subjects for each response to the question for categorical data, and 6-number statistics for continuous data.

3.5.4 Pregnancy History

Pregnancy history data includes only 2 parameters:

- Number of times subject has been pregnant
- Date last pregnancy ended.

The first parameter will be summarized by 6-number statistics and also categorically (as 0, 1, 2, 3, etc.) for ITT subjects. The second one's Year part (e.g., 1998) will be used to get “Number of years since the last pregnancy ended”, which is to be approximated as 2017 – Year of last pregnancy ended. Then the “Number of years since the last pregnancy ended” will be summarized by 6-number statistics.

3.5.5 Substance Use

Substance use include tobacco, alcohol, and illicit drugs. Categorical responses, e.g., “Never”, “Current”, or “Former”, will be summarized by number and percentage of ITT subjects in each response/category by treatment group and for all subjects.

3.5.6 Prior Medications

All medications taken by the subject for one month prior to randomization (pre-study) and during the study will be recorded on the prior and concomitant medication CRF page. Prior medications are medications that were taken up to one month before randomization, and concomitant medications are medications taken on or after the subject was randomized.

Medications will be coded to the therapeutic drug classes and generic drug names by using the World Health Organization (WHO) Drug Dictionary, March 2016 version. The codings will be reviewed by qualified medical personnel, and then summarized by treatment group and for all subjects with the number and percentage of ITT subjects who had prior medications that were coded to each generic drug name and therapeutic drug class, as well as the number and percentage of subjects who had at least one prior medication. Subjects reporting more than one drug in each drug class/generic name are only counted once to that drug class/generic name.

Prior medications will be also be summarized by the descending order of frequencies (total number of ITT subjects) for drug class (i.e., no generic drug names provided).

For the purpose of assessing prior and concomitant medications, the following rules will be used for partial or missing medication start and stop dates.

D=Day, Y=Year, M=Month

Parameter	Missing	Comments	Imputation
Start date	D only	M and Y same as M and Y of first dose of study drug	Date of first dose of study drug
		M and/or Y not same as date of first dose of study drug	First day of month
	M and D	Y same as Y of first dose of study drug	Date of first dose of study drug
		Y not same as Y of first dose of study drug	Use Jan 01 of Y
	M, D, and Y	None - date completely missing	Day prior to date of first dose of study drug

Stop date	D only	M and Y same as M and Y of last dose of study drug	Date of last dose of study drug
		M and/or Y not same as date of last dose of study drug	Last day of month
	M and D	Y same as Y of last dose of study drug	Date of last dose of study drug
		Y not same as Y of last dose of study drug	Use Dec 31 of Y
	M, D, and Y	None - date completely missing and NOT ongoing	Date of last dose of study drug

3.6 Concomitant Medications

As defined in the above [Section 3.5.6](#), concomitant medications are medications taken on or after the subject was randomized to study treatment. Similar to prior medications, concomitant medications will be summarized for Safety populations by the number and percentage of subjects in each coded drug name and drug class. They will also be summarized by the descending order of frequencies (total number of Safety subjects) for drug class (i.e., no generic drug names provided).

A medication may be both “prior” and “concomitant” if a subject took it prior to the randomization (pre-study) and also used it again on/after randomization. Another summary table with unique number and percentage of subjects for each treatment group and all subjects will be presented for medications belonging to both “prior” and “concomitant” (i.e., a medication will not be included in the table unless a subject took it before randomization as well as on or after randomization).

3.7 Efficacy Analyses

The mITT population will be used to compare both the test and reference products to placebo. The PP population will be used to evaluate therapeutic equivalence between the test and reference product.

3.7.1 Primary Efficacy Analyses

Primary efficacy endpoint is the “Clinical Cure” at the Test of Cure (TOC) visit (Visit 3) and includes the following 3 parameters from the “Study Procedure” CRF page:

- Resolution of the abnormal vaginal discharge to a normal physiologic discharge, which is from the variable *SPCDBV* (*Was there clinical diagnosis of bacterial vaginosis?*), with value of “No”
- Negative whiff test, which is from the variable *SPWWT* (*Was there a positive whiff test after adding a drop of 10% KOH to vaginal discharge?*), with value of “No”

- Presence of clue cells at < 20% of the total epithelial cells on microscopic examination of the saline wet mount, which is from the variable *SPSWM*, with value of "No".

To investigate therapeutic equivalence, the 90% confidence interval (CI) for difference, [test - reference], in proportion of subjects achieving "Clinical Cure" will be calculated, using the PP analysis population. Adopted from [FDA Office of Generic Drugs Draft Product Specific Guidance for Generic Drug Development on Metronidazole \(Recommended April 2013\)](#) document, the compound hypothesis to be tested here is:

$$H_0: p_T - p_R \leq -0.20 \text{ or } p_T - p_R \geq 0.20$$

versus

$$H_A: -0.20 \leq p_T - p_R \leq 0.20$$

where p_T = cure rate of test treatment and p_R = cure rate of reference treatment.

Let

n_T = sample size of test treatment group

$c n_T$ = number of cured subjects in test treatment group

n_R = sample size of reference treatment group

$c n_R$ = number of cured subjects in reference treatment group

$$P_T = c n_T / n_T, \quad P_R = c n_R / n_R,$$

$$\text{and } \text{se} = (p_T(1 - p_T)/n_T + p_R(1 - p_R)/n_R)^{1/2}$$

The 90% confidence interval for the difference in proportions between test and reference was calculated as follows, using Yates' correction

$$L = (p_T - p_R) - 1.645 \text{ se} - (1/n_T + 1/n_R)/2$$

$$U = (p_T - p_R) + 1.645 \text{ se} + (1/n_T + 1/n_R)/2$$

If the lower limit $L \geq -0.20$ and upper limit $U \leq 0.20$, we will reject null hypothesis H_0 and claim the bioequivalence ("Therapeutic Equivalence") of test treatment GDC-229 and reference treatment.

Two-sided 90% confidence interval (CI), with continuity correction, for the "Clinical Cure" rate of each treatment arm will also be presented, with the following formula:

$$\hat{p} \pm (z_{\alpha/2} \times se(\hat{p}) + (1/2n))$$

where p is the percentage (proportion) of subjects with “Clinical Cure”, $z_{\alpha/2}$ is the standard normal distribution’s 5th percentile (with $\alpha = 0.1$), and n is the analysis population size in the relevant treatment group, with standard error for the proportion.

$$se(\hat{p}) = \sqrt{\hat{p}(1-\hat{p})/n}$$

PROC FREQ (SAS 9.4) will be employed for the analysis. Proportion of subjects with “Clinical Cure” in test product GDC-229 and reference drug will also be compared against that in placebo group, and p values from chi-square test, or Fisher’s exact test - if any cells have expected frequency of < 5, will be presented. As a parameter for determining adequate study sensitivity, both test product and the reference drug need to have higher “Clinical Cure” rates than placebo and with p values < 0.05, using the mITT analysis population and Last Observation Carried Forward (LOCF), which means if no assessments are available at End of Trial visit (either Visit 3 for completers, or Early Termination (visit 4) for discontinued subjects), then the Visit 2 assessment results will be used. A 95% CI for the “Clinical Cure” rate of each treatment arm will be presented for mITT subjects. The formula for this 95% CI will be the same as above 90% CI except for replacing the α value with 0.05.

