2.5 Sample Size Consideration

Assuming the test and reference products’ Clinical Cure rates are within 4% of each other, the placebo clinical cure rate is 20%, the test and reference clinical cure rates are at least 36.0% and 12.4% of randomized subjects do not qualify for the modified Intent-to-Treat (mITT) population (defined in [Section 3.4](#) of this SAP), then 603 subjects will be required to achieve at least 90% power for superiority and therapeutic equivalence (Schwebke 2015; Chavoustie 2015). However, the previous studies that were used to estimate effect size had significant differences in study design and definition of primary endpoint. Taking these differences into consideration, approximately 738 subjects were planned to be randomized. The assumption of a 36% test and reference clinical cure rate was derived after review of the FDA’s Statistical Review of Metronidazole vaginal gel 1.3% (Center for Drug Evaluation and Research 2014).

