3.4 Analysis Populations

All Screened Population: all subjects who signed Consent Form and screened at the study sites.

Intent-to-Treat (ITT) Population: All randomized subjects.

Safety Population: All randomized subjects who received at least 1 dose of study drug. If the drug accountability is unknown (e.g., due to being lost to follow-up after being randomized) then subjects will be assumed to have taken study drug and included in the safety population. Subjects reporting 0 doses will be excluded.

Modified Intent-to-Treat (mITT) Population: a subset of the Safety Population who also met all 4 Amsel's criteria at baseline, but excluding those who subsequently demonstrate a positive or indeterminate test result for other concomitant vaginal or cervical infections at baseline (e.g. *C. trachomatis*, *N. gonorrhoeae*) which may interfere with the efficacy assessment for BV, or who have a baseline Nugent's score < 4. If baseline STI value is missing, use the Post-Treatment Assessment Visit infection test result. Subjects without a Nugent's score at baseline will be excluded from the mITT population.

Per Protocol (PP) Population: All mITT subjects except for those who had at least one of the protocol deviations listed below. If lack of efficacy (LOE) is the discontinuation reason and the subject took at least 3 doses, then the subject will be included in PP as a treatment failure and then the 6 protocol deviations below will not exclude those subjects:

1. Used topical or systemic antimicrobial drugs after randomization, this includes the following drug classes: antimycotics, antibacterials, antiprotozoals, gynecological anti-infectives, antiseptics and antifungals.
2. Used non-study vaginal products during the study
3. Did not start treatment within 2 days of randomization
4. Took less than 5 doses of study drug
5. Test of cure visit (V3) was not in the Study Day 22 – 31 window, i.e., Visit 3 was not 21 – 30 days after randomization
6. Test of cure visit (V3) not done

Other important violations that represent material non-compliance with study drug or protocol that would impact the primary and secondary efficacy endpoints will be reviewed prior to database lock (i.e., before unblinding). These will be documented in the Evaluability Memo which will be included in the clinical study report.

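### Optional improvement: the two placebo sensitivity tests are unadjusted although baseline Nugent score and BV history are already collected, so some precision may be given up.

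*SAP*

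**What the plan says.** SAP 3.7.1 (Primary Efficacy Analyses) takes the placebo comparisons from PROC FREQ: "p values from chi-square test", or Fisher's exact test when an expected cell count is below 5. Test and reference must each have a higher clinical cure rate than placebo, with p<0.05, in mITT. Protocol 9.6.1 sets the same two-sided 0.05 criterion and names no test. Randomization is 1:1:1, and neither document names a stratification factor (Protocol 3.5.1, SAP 2.3).

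Two baseline variables are relevant.

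- **Nugent score.** A Gram-stain sample is taken at Visit 1 (Protocol 5.1). SAP 3.4 removes women with a baseline score below 4 from mITT and adds: "Subjects without a Nugent's score at baseline will be excluded from the mITT population".
- **BV history.** SAP 3.5.3 lists the CRF item "Is there a history of Bacterial Vaginosis" and summarizes it descriptively only.

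Baseline Nugent score therefore defines the efficacy population and appears in summary tables. Neither variable enters a treatment comparison.

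Equivalence is handled separately, by a Yates-corrected 90% interval in the PP population. SAP 3.7.1 cites the FDA draft guidance where it introduces that part: "the compound hypothesis to be tested here is".

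**The concern.** The trial can claim adequate sensitivity only if both placebo tests succeed, so the relevant figure is the power to win both together, which is lower than the power of either alone. In a randomized comparison, adjusting for baseline variables that predict the outcome shortens the standard error of the active-minus-placebo difference and corrects for chance imbalance in those variables. If the adjusted result is expressed as a marginal risk difference, the quantity being estimated does not change. Both variables will be in the database whether or not they are used. If either predicts clinical cure, the unadjusted test gives up some precision, and the saving is only one model. The sponsor also concedes that its effect-size sources differed in design and endpoint, so a smaller true effect than planned is possible.

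**Working it through.** **Inputs (SAP 2.5).** Placebo cure rate 20%; active cure rates at least 36%; "Clinical Cure rates are within 4% of each other"; "12.4% of randomized subjects do not qualify for the modified Intent-to-Treat (mITT) population"; 603 women required; about 738 planned. Two-sided alpha is 0.05. The share of outcome variance explained by the covariates (R²) is not in the documents. I assume 0, 0.02, 0.05 and 0.10.

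**Step 1: reproduce 603.** With p1 = 0.36, p0 = 0.20 and mean 0.28:

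n = [1.960·√(2·0.28·0.72) + 1.282·√(0.36·0.64 + 0.20·0.80)]² / 0.16² = 163.4, so 164 per arm.

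With the continuity correction, n' = (n/4)·[1 + √(1 + 4/(n·0.16))]² = 175.7, so 176 per arm. Then 3·176 = 528 and 528/0.876 = 602.7, so 603. The stated figure is reproduced exactly. Without the correction the total would be 562. The SAP does not say whether the placebo chi-square itself is continuity-corrected; the figures below are for the uncorrected test.

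**Step 2: planned size.** 738·0.876/3 = 215.5, taken as 215 per arm in mITT.

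**Step 3: one comparison, unadjusted.** SE under the null = √(0.4032/215) = 0.0433. SE under the alternative = √(0.3904/215) = 0.0426. (0.16 − 1.960·0.0433)/0.0426 = 1.763, which gives power of 96.1%.

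**Step 4: both comparisons.** The shared placebo arm gives a correlation of 0.16/0.3904 = 0.41. The bivariate normal probability that both tests succeed is 92.9%.

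**Step 5: adjustment.** Multiply both standard errors by √(1 − R²) and repeat. The effective size per arm is 215/(1 − R²).

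| Assumed R² | SE reduction | Effective gain per arm | Power, one test | Power, both tests |
|---|---|---|---|---|
| 0 | 0 | 0 | 96.1% | 92.9% |
| 0.02 | 1.0% | about 4 women | 96.4% | 93.4% |
| 0.05 | 2.5% | about 11 women | 96.9% | 94.2% |
| 0.10 | 5.1% | about 24 women | 97.5% | 95.4% |

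**Step 6: smaller effect.** If both active cure rates were 34%, joint power would be 84.0% unadjusted and 84.8% to 88.3% for R² of 0.02 to 0.10. At 32% it would be 69.6%, against 70.7% to 75.2%.

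**Step 7: is there a price if the covariates are useless?** In simulation at 215 per arm (6,000 trials per setting), type I error was 4.8–5.1% for the adjusted test and 4.7–5.0% for the chi-square. With no prognostic effect, power for one comparison was 96.1% adjusted and 96.2% unadjusted. The Monte Carlo standard error is about √(0.05·0.95/6000) = 0.3 points for type I error and about the same for power, so these differences are within noise.

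**Step 8: a different adjusted method.** A stratified Cochran-Mantel-Haenszel simulation at N = 738 used two assumed binary prognostic factors. Single-comparison power went from 96.3% to 96.8% when each factor had an odds ratio of 2 (R² about 0.03–0.05). It went from 96.1% to 97.2% at an odds ratio of 3 (R² about 0.07–0.10). This agrees with Step 5.

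**The case against.** The strongest reply is that nothing is wrong. The chi-square test is valid under randomization, is consistent with the two-proportion sizing, and omits no named stratification factor. Its type I error already allows for chance imbalance. The sponsor dealt with uncertainty by raising the sample from 603 to 738, so the remaining gain in joint power is 0.5 to 2.5 points on about 93% for R² of 0.02 to 0.10. All of this stands.

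It also stands that neither document shows that Nugent score or BV history predicts clinical cure. Every woman in mITT met all four Amsel criteria and has a baseline Nugent score of 4 to 10, and this narrowed range may weaken the score as a predictor. A reader might infer that the plan certainly loses precision. The documents do not support that, because at R² = 0 there is no gain.

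A second tempting inference is that the cited guidance governs only the equivalence test and so leaves the placebo tests open. Protocol 3.2 says the guidance includes recommendations for statistical analyses, and Protocol 7.3 says the design leaned heavily on FDA draft guidance. The guidance is not among the documents, so what it recommends for the placebo tests cannot be settled here. Neither document attributes an unadjusted placebo test to it, and Protocol 9.6.1 leaves the method open.

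Finally, the documents do not say how complete BV history will be. A complete-case model could drop women from mITT, so the change needs a rule for this.

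**Conclusion.** The point holds as an optional improvement. The placebo tests are unadjusted, the two covariates are already collected, and Nugent score cannot be missing in mITT. At the planned size, with cure rates of 36%, 36% and 20%, adjustment would raise joint power from about 92.9% to between 93.4% and 95.4% if the covariates explain 2% to 10% of outcome variance. If they explain nothing, it brings no gain and no material loss. The gain would be larger if the active cure rates fell below the planning value. These figures rest on the assumed R², on a normal approximation that applies the same variance reduction to every arm, and on the SAP's planning rates. A reader should not infer that the planned test is invalid, that the trial is underpowered for sensitivity, or that the equivalence analysis is affected. The documents support none of these.

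**What to change.** Before the treatment code is broken, amend the placebo-comparison text of SAP 3.7.1 as follows.

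- **Main test.** In mITT, with the outcome defined as now, fit a logistic model with arm, baseline Nugent score (continuous) and BV history (yes/no). Standardize it to a marginal risk difference for each active arm against placebo, with a robust standard error, and test at two-sided p<0.05. Do not use the conditional odds ratio, which would change the estimand.
- **Missing BV history.** Code it as its own category so that every mITT woman stays in the analysis.
- **Model failure.** If the model does not fit, drop BV history. If it still does not converge, use the planned chi-square or Fisher test.
- **Sensitivity analysis.** Report the unadjusted chi-square or Fisher result alongside.
- **Unchanged.** The Yates-corrected 90% interval in PP remains the equivalence criterion.

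The cost is a paragraph of SAP text and one extra model, with no new data, visits or subjects. The downside is that the main p-value can no longer be checked by hand from a 2×2 table, although the sensitivity result still can.

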5.3 Test of Cure Visit (Visit 3)

The Test of Cure Visit (Visit 3) will occur 21 to 30 days after Visit 1. This is the last visit of the study. The following will be completed:

- Perform physical examination.
- Obtain vital signs after sitting for 5 – 10 minutes ([Section 4.5](#)).
- Measure weight.
- Perform urine pregnancy test.
- Perform pelvic examination including vaginal wall inspection (a naked eye inspection), examination of the cervix, and Investigator's (or designee's) assessment of local site reactions.
- Record subject-assessed local site reactions (e.g., itching, burning/stinging, localized pain).
- Collect a swab sample for central laboratory Nugent's analysis for BV via Gram stain.
- Determine clinical cure of BV by assessing the subject for presence of the following three Amsel's criteria:
 - Resolution of the abnormal vaginal discharge characteristic of BV to a normal physiological discharge; AND
 - Negative "whiff test" after addition of a drop of 10% KOH to vaginal discharge; AND
 - Presence of clue cells at <20% of the total epithelial cells on microscopic examination of the saline wet mount.
- Determine if vaginal pH is <4.7, which is part of the assessment of therapeutic cure (defined as clinical cure, vaginal pH <4.7 and bacteriological cure).
- Record concomitant medications taken since the prior visit along with the indications for the medications.
- Assess and record AEs.

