5.4 Early Discontinuation Visit

At any time, if a subject decides to discontinue her participation in the study or is discontinued from the study for any reason, she will be advised to complete Early Termination procedures (i.e., all procedures noted for Visit 3) as an early discontinuation visit. The following will be completed:

- Perform physical examination.
- Obtain vital signs after sitting for 5 - 10 minutes ([Section 4.5](#)).
- Measure weight.

- Perform urine pregnancy test.
- Perform pelvic examination including vaginal wall inspection (a naked eye inspection), examination of the cervix, and local site reaction assessments.
- Record subject-assessed local site reactions (e.g., itching, burning/stinging, localized pain).
- Collect a swab sample for central laboratory Nugent's analysis for BV via Gram stain.
- Clinical test of response of BV will be determined by assessing the subject for presence of these three of the Amsel's criteria:
 - Resolution of the abnormal vaginal discharge; AND
 - Negative "whiff test" after addition of a drop of 10% KOH to vaginal discharge; AND
 - Presence of clue cells at <20% of the total epithelial cells on microscopic examination of the saline wet mount.
- Determine if vaginal pH is <4.7, which is part of the assessment of therapeutic cure (defined as clinical cure, vaginal pH <4.7 and bacteriological cure).
- Study medication will be returned by the subject, including any unused applicators (unless previously collected).
- Record concomitant medications taken since the prior visit along with the indications for the medications.
- Assess and record AEs.

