9.6 Efficacy Analyses

9.6.1 Primary Endpoints

The primary endpoint is the clinical cure at the Test of Cure Visit (Visit 3) and includes the following:

- Resolution of the abnormal vaginal discharge to a normal physiologic discharge
- Negative whiff test
- Presence of clue cells at < 20% of the total epithelial cells on microscopic examination of the saline wet mount

The mITT population will be used to compare both the test and reference products to placebo. The PP population will be used to evaluate bioequivalence between the test and reference products.

To assess adequate study sensitivity the test and references products need to be statistically superior ($p<0.05$, 2-sided) to placebo using the mITT population.

To establish bioequivalence, the 90% confidence interval for the primary endpoint (the difference [test-reference] in clinical cure rate) must be within [-0.20, +0.20], using the PP population.

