2.3 Trial Design

This is a multicenter (with approximately 40 study sites), randomized, double-blind (for both subjects and investigators), vehicle-controlled bioequivalence study with a clinical endpoint. Following completion of the screening procedures, eligible subjects will be randomized in a blinded manner and in a 1:1:1 ratio to one of three treatment arms:

- GDC-229, the test product
- Reference product (metronidazole 0.75% vaginal gel by Oceanside Pharmaceuticals)
- Vehicle (placebo) vaginal gel.

There are three planned study visits as follows:

1. Study entry Visit (Day 1, screening and randomization);

2. Post-Treatment Assessment (Study days 8-15, i.e., 7 to 14 days after randomization), and
3. Test of Cure (Study days 22-31, i.e., 21 to 30 days after randomization).

Though early termination can occur anytime after enrollment, the study generally is up to 31 days in duration for each subject. The study treatment is to be administered intravaginally once daily at bedtime during Study Days 1 to 5.

All procedures and assessments associated with each study visit are shown in the [Appendix 5.1](#) of this SAP. Including a recruitment period of about seven months, the study duration is expected to be approximately eight months.

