2.4 Study Endpoints

2.4.1 Primary Endpoint

The primary study endpoint is “Clinical Cure”, defined as the resolution at the Test of Cure visit of the following three abnormal BV signs included in Amsel’s criteria:

- Return to normal physiological vaginal discharge as determined by the investigator
- Negative whiff test
- The presence of clue cells at <20% of the total epithelial cells on microscopic examination of the saline wet mount.

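### The placebo-superiority tests score an Early Termination exam on any day, or else Visit 2, as the Test of Cure outcome, although cure is defined on Study Days 22-31

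*SAP*

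**What the plan says.** Both documents place the primary endpoint at one visit. Protocol 9.6.1: "The primary endpoint is the clinical cure at the Test of Cure Visit (Visit 3) and includes the following" three components. SAP 2.4.1 says Clinical Cure is "defined as the resolution at the Test of Cure visit of the following three abnormal BV signs", and SAP 2.3 dates the visit: "Test of Cure (Study days 22-31, i.e., 21 to 30 days after randomization". SAP 3.7.1 opens with the same time point.

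Later in SAP 3.7.1, the study-sensitivity tests (test and reference each against placebo, mITT, p < 0.05) use a different time point. The outcome comes from the "End of Trial visit (either Visit 3 for completers, or Early Termination (visit 4) for discontinued subjects". If neither exam is available, "then the Visit 2 assessment results will be used"; Visit 2 takes place 7 to 14 days after randomization.

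Three other passages matter:
- Protocol 5.4 lets the Early Termination exam happen at any time and for any reason, and SAP 2.3 says the same of early termination. Dosing is on Days 1 to 5.
- Protocol 9.2 and SAP 3.4 make early discontinuers in mITT treatment failures only if they lack an assessment. The mITT definition requires neither a Visit 3 nor a visit window.
- SAP 3.4 removes from Per Protocol any woman whose Visit 3 was not done or fell outside Study Days 22-31. The exception is a woman who left for lack of efficacy after at least 3 doses; she stays in as a failure.

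**The concern.** The endpoint has one time point in its definition and another in one of its two main analyses. A woman who leaves on, say, Day 4 or Day 10 with a clear exam is counted as cured at Test of Cure, although nobody knows her status on Study Days 22-31. The Visit 2 step in the same rule has the same defect for women with no later exam.

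These tests are a required condition: both active arms must beat placebo for the study to show adequate sensitivity. If early clearance differs between arms, the rule shifts the active-placebo differences by an amount unrelated to cure at Test of Cure. The plan enforces the window for equivalence and drops it for sensitivity. Protocol section 9 asks for deviations from its analysis to be included in the SAP; the SAP does not identify this change of time point as one.

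**Working it through.** **Reproducing the planned sample size.** Inputs from Protocol 9.1: 36% vs 20%, 90% power, 12.4% lost to mITT; two-sided 0.05 from 9.6.1. The two-proportion formula with continuity correction gives 176 per arm. 176 / 0.876 = 200.9, so 201 per arm, and 3 × 201 = 603, as stated. At 95% power the same formula gives 215 per arm. 215 / 0.876 = 245.4, so 246 per arm, and 3 × 246 = 738, the number randomized. I use 215 mITT women per arm below.

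**How the SAP rule scores a discontinued woman**

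| Exams available | Scored on | Earliest day set? |
|---|---|---|
| Early Termination exam, any day | that exam | no |
| Visit 2 only | Visit 2 | before the Test of Cure window by design |
| none | failure | not applicable |

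**Effect on the difference.** The documents give neither the share of women with only an Early Termination exam (f) nor the clear rates at that exam (qA active, qP placebo). These are my assumptions: f of 2% to 8%, the same in each arm, with 36% and 20% cured among all others.

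- As failures: difference = (1 − f)(0.36 − 0.20).
- SAP rule: difference = (1 − f)(0.36 − 0.20) + f(qA − qP).

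At f = 5%, failure scoring gives 0.342 − 0.190 = 0.152. With qA = 60% and qP = 25%, the SAP rule gives (0.342 + 0.030) − (0.190 + 0.0125) = 0.1695. With the clear rates reversed it gives (0.342 + 0.0125) − (0.190 + 0.030) = 0.1345.

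| f | Failures | SAP rule, 60% vs 25% |
|---|---|---|
| 2% | 15.7 points | 16.4 |
| 5% | 15.2 | 17.0 |
| 8% | 14.7 | 17.5 |

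The sign of the shift is the sign of qA − qP. The SAP rule exceeds the planned 16.0 points only if that gap is larger than 16 points.

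**Power per comparison at f = 5%** (exact binomial enumeration, uncorrected chi-square, significant in favour of active): 0.950 as failures, 0.975 under the SAP rule with 60% vs 25%, and 0.873 under the SAP rule with 25% vs 60%.

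**False positives.** Suppose both active arms equal placebo at Test of Cure (20%), with early clearance still 60% vs 25%.

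| f | One comparison | Both actives beat placebo |
|---|---|---|
| 0 | 2.5% | 0.5% |
| 2% | 3.8% | 0.9% |
| 5% | 6.6% | 1.9% |
| 8% | 10.5% | 3.6% |

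At f = 5%, clear rates from 50% vs 20% to 70% vs 30% give 5.8% to 7.4% per comparison. With equal clearance in all arms (for example 40%), the per-comparison rate stays at 2.5%.

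**Distance from the threshold.** With placebo at 43/215, 60 active cures give p = 0.055 and 61 give p = 0.043, so one woman can decide a borderline result. At the planned effect (about 77 vs 43), 77 − 60 = 17 active cures, 8% of the arm, would have to become failures to lose significance.

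**The case against.** **The protocol does not forbid using this exam.** Section 5.4 orders all Visit 3 procedures at early termination, including the Nugent swab, and the failure rule reaches only women without an assessment. This stands. A reader might infer from the labels that the protocol does not regard the exam as a cure assessment: 5.3 says "Determine clinical cure of BV by assessing the subject for presence of the following" criteria, while 5.4 says "Clinical test of response of BV will be determined by assessing the subject". The difference in wording is real but does not carry that conclusion. The conflict is with the time point in the endpoint definition.

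**The direction is not known.** A reader might infer that the rule necessarily inflates the active-placebo difference. The documents do not support that: they give no early clearance rates, clear exams on placebo count too, and the reversed case lowers power. Women who leave for lack of efficacy would mostly be non-cures under either rule.

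**Failure scoring is not the truth either.** At f = 5% it lies 0.8 points below the planned 16.0, and the SAP rule with 60% vs 25% lies 1.0 above. This stands. Failure scoring has the advantage of not claiming a Test of Cure success that nobody observed.

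**The false-positive scenario is narrow.** It needs a drug that clears signs early and has no effect at Test of Cure, and success requires both comparisons. The joint column is therefore the relevant one for the study-level criterion.

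**The discharge wording in 5.4 might look like a second definition of cure**, because it omits the return to a normal physiological discharge. It has no shown effect on the analysis: SAP 3.7.1 takes this component from a single CRF variable.

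**Conclusion.** The concern holds as a mismatch between the defined time point and the scoring rule for the mITT placebo tests. No section sets a window for Early Termination exams or scores early ones as failures. Under the stated assumptions (215 per arm, 5% with only an Early Termination exam, 60% vs 25% clear), the SAP rule moves the difference from 15.2 to 17.0 points. If both actives equal placebo at Test of Cure, it raises the both-actives false-positive rate from 0.5% to 1.9%. With clearance reversed it costs power, 0.873 against 0.950. All of this rests on exit and clearance rates that the documents do not give.

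At the planned rates the decision would rarely change. The Per Protocol equivalence test is largely unaffected, because it excludes a missing or out-of-window Visit 3, apart from the lack-of-efficacy exception, which is scored as failure. The change should be made, but the plan does not fail without it.

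**What to change.** In SAP 3.7.1, state for the primary mITT test that an Early Termination exam counts as the Test of Cure outcome only if done on Study Days 22-31. Women with only earlier exams, whether Early Termination or Visit 2, are scored as treatment failures. Both kinds of exam must be treated alike: if only the Early Termination step changed, a woman with a clear Visit 2 and a clear Early Termination exam on Day 18 would be a failure, while one with the clear Visit 2 alone would be a cure.

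This follows the approach of Protocol 9.2 and SAP 3.4 to discontinuers without an assessment, but extends it, so SAP 3.4 should say that the assessment meant is one in the Test of Cure window. Keep the current Early Termination and Visit 2 scoring as a labelled sensitivity analysis, and report the number of women affected in each arm.

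The cost is a change of wording and one derivation line based on exam dates. Cure rates fall slightly; at f = 5% with 60% vs 25% clearance, power per comparison is about 95% rather than 97.5%.
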